## **1. INTRODUCTION**

### **1.1 Rationale**

It is known that cardiovascular disease (CVD) associated with atherosclerosis is the major cause of morbidity, disability and mortality in developed countries and, according to WHO estimates, in the next decade, CVD may become the leading cause of death in developing countries as well [1]. At the same time, the CVD epidemic is unfolding in the setting of significant advances in the diagnosis and treatment of these conditions. One reason for such a dramatic increase in heart attack, stroke, and heart failure incidence is thought to be the steadily aging population. It is due to the fact that age-related changes of blood vessels are an important risk factor for CVD. Growing evidence has been accumulated that aging-related changes in the vascular wall produce metabolically and enzymatically active environment that promotes initiation and progression of vascular disease. The more pronounced the age-related vascular wall changes are, the easier and faster atherosclerosis, hypertension and other CV disorders develop, which, in turn, accelerates the age-related changes.

The main signs of vascular aging include arterial wall thickening, subclinical atherosclerosis, vascular calcification and increased arterial stiffness, of which the increased vascular stiffness is a key sign of vascular aging [2, 3]. It is known that aside from hypertension, the chronic indolent inflammation associated insulin resistance plays a fundamental role in the increase of vascular wall stiffness [4]. In recent years, more data have been accumulated on the role of cellular senescence in the development of vascular aging. One of the major theories of cellular senescence is based on the telomere shortening. A telomere is a region of repetitive nucleotide sequences (TTAGGG) at the end of a linear chromosomal DNA. The main mechanism for maintaining telomere length is the restoration of telomere repetitive DNA sequences by the enzyme telomerase. The assessment of telomerase enzyme activity in combination with other parameters enables to evaluate the rate of aging [5, 6]. Accelerated

telomere shortening and reduced telomerase activity may be due to oxidative stress, chronic inflammation and their associated processes, e.g., insulin resistance [7, 8].

It is believed that vascular and cellular markers of aging may be a useful additional criterion for evaluation of long-term effectiveness of therapy for chronic non-infectious diseases, e.g., arterial hypertension.

The postmenopause is a period in a woman's life that is characterized by accelerated aging processes, higher risk of hypertension and progressive insulin resistance.

There is no doubt that the search for effective targeted therapy of the main chronic non-infectious diseases aimed at not only treatment of the disease but also at slowing of the aging itself is a very promising research area.

Earlier clinical trials revealed a positive effect of moxonidine on insulin resistance suggesting that the drug may be a promising antihypertensive agent with a potential effect on cellular and vascular aging [9].

Other antihypertensive drugs have a short-term effect on the functional state of the arterial wall (owing to smooth muscle relaxation) and a long-term effect on its structure (primarily due to quantitative and qualitative changes in elastin and collagen). A meta-analysis based on the results of 15 randomized clinical studies has demonstrated that the arterial stiffness may be reduced in patients administered with antihypertensive medications regardless of the intensity of the antihypertensive effect [10].

Reduction of arterial stiffness in hypertensive patients was noted for ACE inhibitors, beta blockers (BB), angiotensin II receptor blockers, and calcium antagonists [11].

Along with hypertension, **osteoporosis** is one of the most pressing problems of women's health. Among all known forms of osteoporosis, the postmenopausal osteoporosis accounts for 85% of all osteoporosis cases. As we age, the bone metabolism is shifted towards bone resorption that leads to osteopenia, and to osteoporosis in subjects predisposed to rapid loss of the bone mass [12]. Bone strength depends on the amount of bone mass and quality of the bone tissue. Bone mineral density (BMD) is the measure of bone mass, while the bone tissue quality is characterized by bone turnover that is evaluated with biochemical markers of bone formation (e.g., osteocalcin, OC) and bone resorption (e.g., collagen type 1 C-telopeptide, CTx).

Several experimental studies have demonstrated that moxonidine may lower the activity of Na+- independent Cl/bicarbonate exchanger (anion exchanger, AE) which plays an essential role in viability of osteoclasts that are crucial for bone resorption. The suppression of AE proteins activity has been proven to inhibit osteoclast activity and reduce bone resorption whereas the moxonidine molecule is known to reduce the AE protein activity. Therefore, the results of experimental studies have shown the ability of moxonidine to inhibit bone resorption through its effect on the osteoclast activity. Furthermore, the experimental studies demonstrated the ability of moxonidine to slow down the loss of the bone mass in laboratory animals which lays a foundation for clinical investigation of moxonidine effects on bone tissue density [9].

The discovery of the signaling system that includes receptor activator of nuclear factor  $\kappa\beta$  (RANK), its ligand (RANKL) and osteoprotegerin (OPG) acting as a main regulator of differentiation, functioning and apoptosis of osteoclasts, has made a breakthrough in the understanding of pathophysiology of osteoporosis. RANKL is produced by cells of osteoblast lineage, bone marrow stromal cells, synovial cells and activated T-cells. RANKL binds to OPG and plays the coordinating role in osteoclastogenesis, osteoclasts differentiation, activation and apoptosis. RANKL activation is an important preliminary step in osteoclast production and occurs with RANKL binding to pre-osteoclasts. OPG is a natural decoy receptor for RANKL and competes with RANK for binding RANKL. By blocking such binding, OPG suppresses bone resorption in favor of bone formation. The abnormal binding of RANKL to OPG is an essential link in the pathogenesis of many diseases associated with increased production of RANKL and increased bone resorption [13].

Vascular wall calcification is the most important aspect of the age-related changes. A number of studies have established that there is a clear inverse correlation between the degree of vessels calcification and the level of bone mineralization. This phenomenon was called the calcification paradox. Once the key proteins that stimulate or inhibit the extraskeletal calcification have been discovered, it has become clear that the vascular calcification is not only a passive process of calcium and phosphorus deposition but also an active process that involves vascular “ossification”. Numerous authors have confirmed the association between osteoporosis and vascular calcification in a general population [14].

Of all the components that most clearly indicate the link between bones and arterial wall, OPG attracts major attention. OPG is a part of a system whereby the osteoblasts modulate the osteoclastogenesis.

Increased OPG levels have been found in postmenopausal women with osteoporosis versus healthy women of corresponding age. It is suggested that the increased OPG level is a compensatory reaction to the increased osteoclast-mediated bone resorption. Normally, RANKL is not expressed in the vessels, however, its expression was found in OPG-deficient mice and in aortic valves of patients with calcified aortic valve stenosis. The elevated RANKL may be a link between bone tissue and vascular calcification [15].

All the above data suggest that the broadening of knowledge about OPG effects on the arterial wall and bones allows us to understand clinical and therapeutic value of OPG in osteoporosis and vascular calcification.

Published data contain information on positive effects of beta-blockers on the bone tissue condition. There are data which clearly demonstrate a positive effect of beta-blockers on bone mass. Thus, Australian researchers in a large-scale 20-year-long study involving 3488 patients have shown that a regular intake of beta blockers (BB) can increase bone mineral density (BMD) and prevent osteoporosis in 50% of patients [16].

In the population-based study of women older than 50 years (Geelong Osteoporosis Study), the association between beta blockers treatment and bone mineral density (BMD) or bone fractures has been estimated. The results have confirmed the association between the treatment with beta blockers and high level of BMD or low risk of bone fractures [16].

However, there are other studies that failed to confirm a positive effect on beta blockers on BMD (Study of Osteoporosis Fractures, Danish Osteoporosis Prevention Study, EPIDOS, Rotterdam Study). These studies pursued other goals and the effects of beta blockers on BMD were analyzed retrospectively. The analysis of the beta blockers efficacy was also complicated by the fact that the investigated group and the comparative group of patients differed from each other greatly in confounding factors that may have affected the amount and quality of the bone tissue (body mass, hormonal replacement therapy, smoking, statins and glucocorticoids treatment, etc.). Thus, there is currently no sufficient clinical experience to draw definitive conclusions about effects of beta blockers on BMD.

The proposed trial is a comprehensive study of moxonidine effects on processes of cellular and vascular aging as well as bone metabolism. We may not rule out a possible role of moxonidine in formation of calcification paradox.

## **2. PROGRAM OBJECTIVES**

**2.1 Primary objective:** To investigate the effect of moxonidine versus bisoprolol on collagen type 1 C-telopeptide in postmenopausal female patients with arterial hypertension and osteopenia.

### **2.2 Secondary (experimental) objectives:**

To investigate the effect of moxonidine versus bisoprolol on bone metabolism and bone tissue density in postmenopausal female patients with essential hypertension and osteopenia.

To investigate the effect of moxonidine versus bisoprolol on the processes of cellular and vascular aging in postmenopausal female patients with essential hypertension and osteopenia.

To investigate efficacy of antihypertensive therapy with moxonidine versus bisoprolol in hypertensive postmenopausal women.

## **3. PROGRAM PLAN AND PROCEDURES**

### **3.1 General design**

This is explorative, randomized, open-label, interventional, comparative clinical trial.

Study population is postmenopausal women with essential hypertension and osteopenia. The study will enroll 114 patients after screening (it is expected that 300 patients will need to be screened in order to reach this enrollment goal).

After the informed consent signing, the patient's participation in the study will include the period before the studied product administration, the treatment period and the final visit.

Patients will be randomized to one of two groups: moxonidine group or bisoprolol group.

According to the study protocol, patients randomization to the control and investigated groups will be carried out using a simple envelopes method and, therefore, it is assumed that the control and the investigated groups will be matched by the basic measured parameters; the number of subjects in the main and control groups is planned to be equal.

The study endpoints are measured prior to the studied product initiation (V1) and after completion of 48-week treatment with the investigated product (V4).

The period prior to the studied treatment initiation is designed to assess the patient meeting inclusion criteria and to carry out 7-10-day washout period in patients with previous antihypertensive therapy. The planned duration of the period before the treatment initiation does not exceed 14 days after the signing of the informed consent form by the patient.

Then, at the enrollment visit during the treatment period, the investigator will assess the patient meeting the inclusion criteria. If the inclusion criteria are met, the patient will be enrolled in the study. The baseline condition data will be obtained from the patient, and then the patient will be randomized to one of the two treatment groups (moxonidine or bisoprolol). The treatment period involves the enrollment visit (V1), and 3 more visits.

The final visit 4 is carried out at week 48 after the enrollment visit, the patient then completes the study.

The patients' treatment includes gradual titration of the studied products doses.

Group 1 will receive moxonidine with the dose titrated to a maximum, and then, if necessary, the patient will be shifted to the combination therapy (Step 2 – adding an ACE inhibitor)

[figure not shown]
Group 2 will receive bisoprolol with the dose titrated to a maximum, and then, if necessary, the patient will be shifted to the combination therapy (Step 2 – adding an ACE inhibitor).

After randomization to moxonidine and bisoprolol groups (V1), patients start treatment with 0.4 mg moxonidine QD or 5 mg bisoprolol QD. If the target BP (<140/90 mmHg) is reached in 2 weeks, the patient continues taking the medication at the same dose. If the target BP is not reached in 2 weeks, the moxonidine dose is increased to 0.6 mg QD, the dose of bisoprolol is increased to 7.5 mg QD. If the target BP is not reached in 2 weeks of treatment with the increased doses, an ACE inhibitor (perindopril) at a dose of 10 mg/day is added at the 8th week of the study. In case of intolerance to perindopril, losartan at a dose of 50 mg/day will be administered.

During the study, the patient will have parameters of efficacy, tolerability and safety of the therapy with moxonidine or bisoprolol regularly assessed.

The study design is shown in Figure 1.

Figure 1. The overall study design

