### 3.4 Schedule of the study procedures

Prior to the study enrollment, examination to assess conformity with the inclusion/exclusion criteria, to obtain baseline data and ensure washout period (if necessary) will be carried out for a patient. After enrollment and initiation of the investigated treatment, the study procedures will be conducted to assess product tolerability, safety, efficacy and patient compliance. All scheduled visits are mandatory. Washout period will be carried out only for patients with prior antihypertensive therapy. Each patient is to sign the informed consent prior to any study activities including screening / “examination to assess conformity with the in- and exclusion criteria.

Schedule of the study procedures is presented in Table 2.

	Visit 0 Screening	Visit 1	Visit 2	Visit 3	Visit 4
	Day-14...-1	Day 0	Week 8	Week 24	Week 48
Drug administration		+	+	+	+
Dose titration / treatment adjustment		+	+	+	
BP / HBR / Patients' diary analysis	+	+	+	+	+
ECG, K, Na	+			+	
Creatinine	+			+	
ALT/AST	+			+	
Parathyroid hormone	+				
X-ray densitometry, BMD	+				+
Total calcium, Phosphorus	+			+	+
PWV		+			+
IMT + evaluation of subclinical atherosclerosis		+			+
Telomerase activity		+			+
Osteocalcin		+		+	+
Collagen type 1 C-telopeptide		+		+	+
Osteoprotegerin, RANKL		+			+
Safety Information	+	+	+	+	+

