### **3.6.5 Visit 3 (V3)**

The investigator will document the disease history since the last visit, including all adverse events, changes in concomitant treatment, changes in concomitant medications doses, if any.

The investigator will analyze the effectiveness of the therapy according to the patient's BP self-monitoring diary data.

The investigator measures BP and HR according to the ESH/ESC recommendations that are listed in Appendix 1. Blood pressure and heart rate are measured in a sitting position after 5 minutes of rest. **Two** measurements are done, the average value of the measurements is documented. BP is measured on the same arm during the entire study.

Fasting blood sampling will be carried out for the following tests: BMP (potassium, sodium, creatinine, total calcium, inorganic phosphorus, ALT, AST), hormonal test (PTH) and bone metabolism tests, including osteocalcin, Ctx, OPG, RANKL.

The investigator evaluates response to the treatment (target BP reaching), documents it in source documents and decides on further treatment of the patient. If target BP has not been reached, the patient's investigated product dose is titrated according to the study design. If the target BP has been reached, the patient continues with the current treatment until the next visit.

The investigator analyzes the patient's compliance based on the number of returned tablets. The investigator will provide the patient with the investigated medications and invite the patient to the next visit (visit V4) scheduled for week 48 after the enrollment visit (336 days  $\pm$  5 days after the enrollment visit); the patient will be asked to return the investigated medication blisters (empty, started and not started blisters). The patient will be instructed to start taking the provided product the next day morning, 1 tablet per day. The patient will be instructed to report any adverse events (if applicable) to the investigator.

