**Table 2. Method and frequency of laboratory testing**

Test	Parameters	Laboratory	Method	Frequency
Blood biochemistry	Creatinine* Potassium Sodium ALT AST Total calcium Inorganic phosphorus	Site	Adopted at the hospital center	2x: visits V0 and V3
Blood biochemistry	Total calcium Inorganic phosphorus	Site	Adopted at the hospital center	3x: visits V0, and V3, V4
Hormonal blood test	Parathyroid hormone	Site	Adopted at the hospital center	1x: visit V1
Bone metabolism	Osteocalcin Ctx	Site	Adopted at the hospital center	3x: visits V1, V3, V4
	OPG RANKL	Site	Adopted at the hospital center	2x: visits V1, V4

\*Creatinine clearance (CC) is calculated by **Cockcroft-Gault** equation on visits V0 and V3:

$$\text{CrCl} = (140 - \text{age}) \times \text{IBW} / (\text{Scr} \times 0,792) \quad (\times 0.85 \text{ for females})$$

If creatinine was measured in mg/dl, to convert the value to mkmol/L it should be multiplied by 88.4.

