#### **Secondary Endpoints:**

- To assess mean values of osteocalcin at visit 4 versus baseline level (visit 1) and to compare the values between the groups
- To assess mean values of the receptor activator of nuclear factor kappa-B ligand (RANKL) at visit 4 versus baseline level (visit 1) and to compare the values between the groups
- To assess mean values of BMD at visit 4 versus baseline level (visit 1) using control dual-energy X-ray absorptiometry and to compare the results between the groups
- To assess mean telomerase activity at visit 4 versus baseline level (visit 1) and to compare the values between the groups
- To assess mean pulse wave velocity (PWV) at visit 4 versus baseline level (visit 1) and to compare the values between the groups
- To assess mean intima-media thickness (IMT) at visit 4 versus baseline level (visit 1) and to compare the values between the groups
- To estimate the proportion (%) of patients who achieved target blood pressure <140/90 mmHg at the visit 2 (Week 8), 3 (Week 24) and 4(Week 48) and according to the patient's diary.

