#### **10.2 Procedures for accounting for missing, unanalyzable and questionable data**

In case of missing, unanalyzable and questionable data appropriate statistical methods will be applied. Patients who did not complete the planned treatment course will be added to the analysis by the last observation carried forward method.

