**The main indicator of the treatment efficiency:**

Changes in mean values of the bone resorption marker (collagen type 1 C-telopeptide) at the end of the study (V4) from the baseline (V1) in comparison between the groups.

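### The week-24 CTX and osteocalcin values have no settled role: they can enter only by last observation carried forward, which conflicts with the completers-only efficacy rule

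*Combined protocol and SAP*

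**What the plan says.** **Timing.** Section 3.1 states that "The study endpoints are measured prior to the studied product initiation (V1) and after completion of 48-week treatment with the investigated product (V4"). The synopsis (Study Design) and section 3.5 repeat this.

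**Sampling.** The schedule in section 3.4 has a row for "Collagen type 1 C-telopeptide" marked at V1, V3 and V4, and the osteocalcin row is marked the same way. The laboratory table in section 3.7 gives the frequency of both as "3x: visits V1, V3, V4". Section 3.6.5 has blood drawn at V3 for "bone metabolism tests, including osteocalcin, Ctx, OPG, RANKL"; the schedule and the laboratory table do not place the last two of these at V3.

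**Endpoints.** The primary indicator in section 10.3 is the change in mean CTX "at the end of the study (V4) from the baseline (V1) in comparison between the groups". The synopsis and sections 3.10 and 6.1 agree. Osteocalcin is likewise defined as V4 against V1.

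**Missing data and populations.** Section 10.2 says: "Patients who did not complete the planned treatment course will be added to the analysis by the last observation carried forward method". Its intention-to-treat set requires data from V3 or V4. Sections 6 and 10.3 place the efficacy analysis in women who completed the study according to protocol.

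**BMD.** Section 3.10 reads "To assess mean values of BMD at visit 4 versus baseline level (visit 1"), but densitometry is scheduled at screening (V0) and V4, and the V1 procedures in section 3.6.2 contain none.

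**The concern.** The primary marker is measured twice on treatment, and the plan does not settle what the first of these measurements is for. Two rules point in opposite directions. Under LOCF, a woman who leaves after V3 contributes her week-24 CTX as if it were her week-48 CTX. Under the completers-only rule, she contributes nothing.

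The design makes such women likely. Tablet counts are made at V3, and low compliance is a reason for withdrawal (sections 3.6.5, 4.5 and 5.5). Blood pressure at or above the protocol's non-response threshold at V3 also leads to withdrawal (section 5.1). Stopping treatment means leaving the study (sections 4.5 and 5.3). These women are at the visit where CTX is scheduled, and their reasons for leaving may depend on the treatment received and may differ between arms in an open-label trial. A completers-only comparison is then no longer protected by randomisation, and LOCF assumes that CTX does not change between weeks 24 and 48.

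At stake is mainly the credibility of the V4 contrast and, to a small degree, its precision. If the role of V3 is left open, it may be chosen after the data are seen.

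**Working it through.** **1. What exists and what is used**

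| Item | V1 | V3 | V4 | Source |
|---|---|---|---|---|
| CTX, osteocalcin drawn | yes | yes | yes | 3.4, 3.6.5, 3.7 |
| CTX, osteocalcin endpoints | yes | no | yes | Synopsis, 3.10, 6.1, 6.2, 10.3 |
| Woman with V3, no V4, under LOCF and ITT | – | carried to V4 | – | 10.2 |
| Same woman under completers-only rule | – | dropped | – | 6, 10.3 |

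Among women who completed to V4, LOCF has almost no one to act on. The two rules cannot both govern the primary analysis.

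**2. Inputs for size**

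- From the documents: 57 + 57 = 114 randomised (section 3.2). Section 10.5 states that no formal sample size calculation was made, so there is no power figure to reproduce.
- Assumed, because the documents give no value: the fraction m with V3 but no V4, equal in both arms, and the baseline-adjusted correlation ρ between V3 and V4 CTX. Everyone is taken to have V3.

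For orientation, m = 5%, 10%, 15% or 20% of 114 is about 6, 11, 17 or 23 women.

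**3. Variance of the V4 contrast**

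With σ² the baseline-adjusted variance and n women per arm, per-arm variances are:

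- V4 completers only: σ² / [n(1 − m)]
- Likelihood model using V3: (σ² / n) × [(1 − ρ²)/(1 − m) + ρ²]

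The ratio of the second to the first is (1 − ρ²) + ρ²(1 − m) = **1 − mρ²**.

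| m | ρ = 0.4 | ρ = 0.6 | ρ = 0.8 |
|---|---|---|---|
| 0 (completers) | 1 | 1 | 1 |
| 0.05 | 0.992 | 0.982 | 0.968 |
| 0.10 | 0.984 | 0.964 | 0.936 |
| 0.15 | 0.976 | 0.946 | 0.904 |
| 0.20 | 0.968 | 0.928 | 0.872 |

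At m = 0.15 the variance cut is about 2%, 5% or 10%. The square roots are 0.988, 0.973 and 0.951, so the standard error falls by about 1%, 3% or 5%. With 114 − 17 = 97 completers, this is worth 97/0.976 ≈ 99, 97/0.946 ≈ 103 or 97/0.904 ≈ 107 completers.

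**4. Bias**

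A baseline-adjusted completers-only comparison needs missing V4 values to be unrelated to V4 CTX given arm and V1 CTX. The longitudinal model allows missingness to depend on V3 CTX as well, which is a weaker condition. LOCF needs no average change after week 24 in those who leave. The documents give no data from which to size or sign either bias.

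**5. BMD**

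V1 is no later than 14 days after consent (section 3.6.2), and the DXA at V0 comes after consent and before treatment. A pre-treatment value is therefore planned for every enrolled woman. Only the visit label in the endpoint text is wrong.

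**The case against.** A single prespecified V4 endpoint is legitimate in a trial that calls itself explorative, and section 10.1 defers detail to a statistical analysis plan finalised before data lock. Both points are fair. They support keeping V4 as primary, but they do not resolve the conflict between sections 10.2 and 10.3, which are both current text.

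Section 4.6 asks women who leave early to complete final-visit procedures if possible, so some will have a late CTX value. This reduces m but does not remove the problem.

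The strongest objection concerns precision. If the per-protocol set is kept, m = 0 and the V3 values add nothing to the V4 contrast. That stands, and it is why the model is of use only together with a change of population.

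Several stronger readings are tempting, and the documents do not support them:

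- *Endpoints are measured at V1 and V4 and nowhere else.* The timing sentence does not say so, and the blood pressure endpoint is assessed "at the visit 2 (Week 8), 3 (Week 24) and 4(Week 48) and according to the patient's diary".
- *The V3 samples enter no comparison.* LOCF and the intention-to-treat definition give them a route. It is closed only if the completers-only rule governs. The samples also come only from women still in the study at V3.
- *Averaging weeks 24 and 48 would sharpen the primary answer.* The standard error factor √[(1 + ρ)/2] is 0.837, 0.894 or 0.949 at ρ = 0.4, 0.6 or 0.8, but this is a different estimand. It gains power only if the week-24 effect is at least 2 × factor − 1, about 67%, 79% or 90%, of the week-48 effect. Nothing in the documents supports that.
- *BMD has no baseline.* It has one, at V0.

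**Conclusion.** The point holds as a gap and a contradiction in the analysis plan. CTX and osteocalcin at week 24 have no planned use except LOCF, and the completers-only rule conflicts with that use. The precision at stake for the V4 contrast is small: a variance cut of mρ², or 2% to 10% at an assumed 15% with V3 but no V4 and ρ between 0.4 and 0.8, and nothing among completers.

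The better reason to act is bias. Withdrawal at V3 is tied to compliance and blood pressure, and a model that uses V3 CTX rests on a weaker assumption than either rule now in the text. It does not remove all bias: withdrawal may depend on things that V3 CTX does not capture, and women who leave before V3 contribute nothing. The BMD and timing-sentence points are housekeeping.

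**What to change.** In section 10.3:

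1. Keep the between-arm CTX contrast at V4 as primary. Estimate it from one longitudinal model with V3 and V4 CTX as outcomes, V1 CTX as baseline covariate, and arm, visit and arm-by-visit terms.
2. Fit it in all randomised women with a V3 or V4 value (the intention-to-treat set of section 10.2), analysed in the arm assigned. For this analysis it replaces both LOCF and the per-protocol restriction. Report the per-protocol result as supportive.
3. Report the week-24 contrast as supportive. Treat osteocalcin in the same way.
4. State how a final-visit sample taken early under section 4.6 is assigned to a visit, so that it is not counted as week 48 by default.

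Housekeeping: align the endpoint-timing sentence in the synopsis and sections 3.1 and 3.5 with the schedule. Reconcile the V3 marker list in section 3.6.5 with the schedule and laboratory table. Label the BMD baseline as the V0 DXA in the synopsis and sections 3.10, 6.2 and 10.3.

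The cost is wording, slightly more analysis and one more supportive contrast per marker. No new samples or visits are needed. It should be settled before data lock.
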